# **Cannabinoid Medication for Adults with OCD**

**NCT02911324**

**1/7/2020**

## Background, Significance and Rationale

### Background, Significance and Rationale

The two first-line treatments for OCD are a class of medications called serotonin re-uptake inhibitors (SRIs) and a type of cognitive behavioral therapy called exposure and response prevention (EX/RP). But more than a third of patients with OCD do not respond to these treatments, and less than half become well. Thus new treatment approaches are needed.

EX/RP is thought to involve fear extinction learning. Recent research suggests that modulators of the cannabinoid system, such as nabilone (a synthetic cannabinoid that is thought to be a CB(1) agonist), may enhance fear extinction learning and therefore could enhance EX/RP. However, nabilone could also work via cortico-striatal circuits (which have high levels of cannabinoid type 1 receptors) directly reducing repetitive behaviors such as those seen in OCD (i.e., compulsions). To test both ideas, we propose a small pilot randomized trial to explore the effects of nabilone on its own for four weeks versus in combination with EX/RP in 20 adults with OCD (10 per arm).

This proof-of-concept study will investigate whether the administration of nabilone in adult OCD patients is feasible and/or well-tolerated. The intent is to collect pilot data to support future grant applications.

## Specific Aims and Hypotheses

### Specific Aims and Hypotheses

The goal of this pilot study is to investigate whether the administration of nabilone in adult OCD subjects is feasible and/or well-tolerated. The intent of this protocol is to gather pilot data.

## Description of Subject Population

### Sample #1

Specify subject population

Adult individuals with OCD

Number of completers required to accomplish study aims

20

Projected number of subjects who will be enrolled to obtain required number of completers

25

Age range of subject population

18-60

Gender, Racial and Ethnic Breakdown

Based on the community from which we will be drawing subjects and proportions to those encountered

during previous clinical trials at this site, we expect the sample to be approximately 5% Hispanic and 95% Non-Hispanic; racially there will be 89% White, 9% Black, 2% Asian. Based upon the prevalence of OCD, it is expected that the sample will be approximately 1:1 =male:female.

Description of subject population

Female and male adults with a diagnosis of OCD and clinically significant symptoms (i.e., a Y-BOCS score of at least 16). Minorities and females will be well represented in this study.

## Recruitment Procedures

Describe settings where recruitment will occur

Recruitment will draw from the broadest possible population with respect to gender and ethnic origin.

Participants will be enrolled through the Anxiety Disorders Clinic, located on the third floor of the New York State Psychiatric Institute.

How and by whom will subjects be approached and/or recruited?

OCD patients will be recruited by a physician or mental health practitioner referrals, or patient or family referrals following advertisement of our work.

How will the study be advertised/publicized?

IRB-approved advertisements and flyers will be posted both online and in the local community (e.g., in and around the CUMC campus). Online advertisements may be posted on websites dedicated to obsessive compulsive disorder or psychiatry research [e.g., our own clinic website ([www.columbia-ocd.org](http://www.columbia-ocd.org)), [www.ocfoundation.org](http://www.ocfoundation.org), Columbia clinical trials website] and on community websites (e.g., [Craigslist.org](http://Craigslist.org), [Myspace.com](http://Myspace.com), [Facebook.com](http://Facebook.com), [Friendster.com](http://Friendster.com), [Livedeal.com](http://Livedeal.com), [Citynews.com](http://Citynews.com), [Adwords.google.com](http://Adwords.google.com), [ResearchMatch.org](http://ResearchMatch.org) and [Topix.net](http://Topix.net)). For web-based forums or discussion groups that are open only to patient members, permission to recruit will be obtained from group leaders prior to posting.

We would like to use RecruitMe for recruitment. RecruitMe is a recruitment website launched by the Clinical Trials Office at Columbia University Medical Center and is meant to connect those that want to participate in research studies to the investigators that conduct them. To begin using RecruitMe, the volunteer will search for a medical condition or research field of the user's interest and answer a few eligibility questions. If the volunteer pre-qualifies for a study, he or she may either reach out directly to the research team or if he/she leaves their contact information a member of that research team will reach out to them. RecruitMe also allows users to join a research registry which will notify users via email whenever a study or clinical trial of interest enters the database. Investigators that join RecruitMe will have the ability to create a profile and submit their study for review. Upon approval from members of the Clinical Trials Office, their study will be visible to users that visit RecruitMe.

Do you have ads/recruitment material requiring review at this time?

No

Does this study involve a clinical trial?

Yes

Please provide the NCT Registration Number

NCT02911324

**Concurrent Research Studies**

Will subjects in this study participate in or be recruited from other studies?

Yes

Describe concurrent research involvement

Will subjects in this study participate in or be recruited from other studies?

Yes. Eligible subjects who have finished other studies in the Anxiety Disorders Clinic will be offered participation if they are eligible. These protocols will include:

IRB#7405 Effects of Marijuana on Symptoms of OCD (provided they test negative for THC after study completion)

IRB#6628. Attaining and maintaining wellness in OCD

IRB#7000. Control and Reward Circuits in OCD

IRB#7127 Toward Precision Medicine for OCD

IRB#7059 Pilot study of personalized-computerized inhibitory control training for OCD

IRB# 6837 Internet Based Treatment for OCD (iCBT)

Participants will be allowed to participate in other studies at our center at the same time if these studies do not involve treatment (e.g. IRB#7127 Toward Precision Medicine for OCD).

Before and after finishing the study, participants will be allowed to participate in other treatment and non-treatment studies at our center if they meet the eligibility criteria for those studies (including time off medication prior to entry).

Subjects will be re-screened if there is a delay of more than 4 weeks between screening and participation (and the physical exam and laboratory tests will be repeated if older than 3 months).

Describe concurrent research involvement

All participants in the current study will be screened under "IRB #7094R- Anxiety Disorders Clinic and Hispanic Treatment Program Screening and evaluation Process."

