**Inclusion/Exclusion Criteria**

Name the subject group/sub sample

Adult OCD subjects

Create or insert table to describe the inclusion criteria and methods to ascertain them

Inclusion criteria	
CRITERION	METHOD OF ASCERTAINMENT
1) Patient must be 18-60 years of age at the time of	Clinical Interview

consent	
2) Patient must be physically healthy and, if female, must be non-pregnant. Females of childbearing potential must comply with contraceptive restrictions noted in the protocol.	Clinical interview and physical examination (including EKG and blood and urine tests) by trained M.D, and as part of screening.
3) Patient must fulfill DSM-5 criteria for OCD, OCD being the principal disorder (i.e., currently the most severe and needing of treatment) and have had OCD for at least one year	Clinical Interview by trained M.D. or Ph.D. and results of SCID
4) Patient with a Y-BOCS score of greater than or equal to 16 prior to entering trial.	Clinical interview and assessment by trained rater
5) Patient is off all psychotropic (except selective SRIs) and other types of drugs likely to interact with nabilone (e.g., antihistamines or anticholinergic drugs). Patients taking a selective SRI must be on a stable dose for 6 weeks prior to study entry. Note: Subjects on clomipramine will be excluded because both clomipramine and nabilone can cause orthostatic hypotension.	Clinical interview
6) Each patient must have a level of understanding sufficient to provide written informed consent to all required study tests and procedures.	Clinical interview
7) Subject must be able to tolerate a treatment-free period	Clinical Interview

Create or insert table to describe the exclusion criteria and methods to ascertain them

Exclusion criteria	
1) History of violence.	Psychiatric evaluation
2) Presence of psychotic symptoms or lifetime history of schizophrenia, bipolar disorder, substance-induced psychotic disorder, or psychosis due to a general medical condition.	Psychiatric evaluation/SCID
3) Presence of developmental disorder or intellectual disability.	Clinical interview
4) Severely depressed patients with HAMD-17 (17-item Hamilton Depression Rating Scale) >25 or judged clinically to be at risk of suicide.	Clinical Interview/SCID and HAMD-17
5) OCD patients with primary symptoms of hoarding	SCID/Y-BOCS check-list
6) Female patients who are either pregnant or nursing.	Clinical interview, medical exam, and blood pregnancy test

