7) Patients planning to commence EX/RP during the period of the study or currently in EX/RP treatment.	Clinical interview
8) Current substance use disorders (meeting criteria within the past year, with the exception of nicotine) or positive urine toxicology at screening, or any adverse reaction to a cannabinoid (e.g., panic attack with THC use).	Clinical interview and urine toxicology.
9) History of any significant medical condition (e.g., hypotension) that might increase the risk of participation given the known side effects of nabilone.	Clinical interview and medical examination

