## Study Procedures

Describe the procedures required for this study

Screening/initial evaluation

Patients deemed eligible following screening (by phone or in person) will undergo with their consent: 1) an evaluation by a senior clinician (M.D. or Ph.D.); 2) a Structured Clinical Interview for DSM-5; 3) a Y-BOCS to assess OCD severity; and 4) a medical evaluation (i.e., history, physical, routine blood tests [including blood pregnancy test for females], urine toxicology, and EKG). Those who meet entry criteria will provide written informed consent.

Randomization and Treatment Intervention

After the baseline evaluation, participants will be randomized to one of two groups. Randomized assignments (stratified by SSRI use) will be generated using a random number generator in SPSS.

Group 1 (n=10) will receive nabilone at 1 mg BID over 4 weeks. (Note: These patients will be offered EX/RP at no cost in open treatment after the 4 weeks of the trial).

Group 2 (n=10) will receive nabilone at 1 mg BID plus therapist-guided EX/RP (as described below) during 4 weeks.

All subjects will meet weekly with a study psychiatrist to receive nabilone and to review side effects.

Those randomized to EX/RP will also meet with a study therapist (MA or PhD-level) to receive 9 sessions of EX/RP (i.e., a treatment planning session plus 8 sessions of EX/RP) over four weeks according to a treatment manual. Following standard procedures, EX/RP will include therapist-aided exposure, self-guided exposure as homework, ritual prevention, and education about relapse prevention.

Assessments (independent evaluator)

An independent evaluator (Master's level or above) who is not involved with study treatment will assess global psychopathology (CGI); OCD symptoms (YBOCS); sensory phenomenon (Sao Paulo Sensory Phenomena Scale), depressive symptoms (HAM-D) **and at follow-up, any changes in treatment since study end and adherence to EX/RP lifestyle**. Subjects will also complete self-reports that assess depression and anxiety (DASS) and quality of life (Q-LES-Q). Subjects will be evaluated at weeks 0, 1, 2, 3, and 4 and also 1 month after study end (week 8, by phone or in person).

You can upload charts or diagrams if any

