## Criteria for Early Discontinuation

### Criteria for Early Discontinuation

Participants are free to withdraw from the study at any time for any reason. Study doctors are to discontinue patients from the study if patients:

- Request early discontinuation or withdraw consent.
- Experience a serious or intolerable adverse event that prevents the patient from continuing.
- In the Investigator's opinion, are experiencing a clinically significant deterioration in OCD (i.e., YBOCS score six points greater than their baseline at any time point).
- In the Investigator's opinion, are experiencing a clinically significant deterioration in a comorbid condition such as major depression. For example, if a patient became suicidal or their symptoms of depression increased such that the depressive symptoms were much or very much worse relative to baseline and the HDRS-17 is no longer <25, they would be discontinued from the study.
- Commit a protocol violation, including lack of compliance.
- Are "lost to follow-up."
- Encounter other conditions (such as administrative issues or pregnancy).

If a patient discontinues from the study at any time at their own request or at the study doctor's discretion, the reason(s) for discontinuation are to be recorded by the study. Subjects will be asked to return to the study site for final safety assessments as scheduled for the final study visit. Patients withdrawing from the study for reasons related to the study medication (usually adverse events) will be followed until the event(s) have resolved or no further action is required.

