## Blood and other Biological Samples

Please create or insert a table describing the proposed collection of blood or other biological specimens  
N/A

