### Risks/Discomforts/Inconveniences

Risks that could be encountered during the study period

Risks associated with assessments:

Patients are assessed in person by experienced clinicians for discomfort or frustration associated with psychiatric interviewing or filling out questionnaires. Study clinicians are skilled at dealing with these events and will make efforts to help clients to feel as comfortable as possible (e.g., by giving breaks during an evaluation, offering encouragement).

Risks associated with EX/RP:

In EX/RP (an evidence-based treatment for OCD), patients confront feared situations that are expected to produce moderate levels of distress initially. This initial fear reaction is essential to the treatment, as it allows the patient to habituate to situations in which he or she is excessively or irrationally fearful.

Risks associated with nabilone: (see package insert):

Chemically, nabilone is similar to the active ingredient found in naturally occurring Cannabis (marijuana) or THC. It is thought to interact with the cannabinoid receptor system in the brain.

According to the package insert approved by the FDA, the most common adverse reactions to nabilone in controlled clinical trials were drowsiness, vertigo, dry mouth, euphoria (feeling "high"), ataxia, headache, and concentration difficulties. Caution is recommended when administering nabilone in combination with any CNS depressant. The effects of nabilone have not been studied in pregnant or nursing women.

Accurate estimates of the estimates of the incidence of adverse events associated with any drug are difficult to obtain because these estimates are influenced by factors such as drug dose and detection technique. The table presented below indicates the relative frequency of adverse events in placebo controlled clinical trials.

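### The re-screening rule lets a delayed patient start nabilone on a blood pregnancy test up to 3 months old, and leaves unclear whether urine toxicology may be equally old

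*Protocol*

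**What the plan says.** The rule is one sentence in the protocol, under Concurrent Research Studies. Its main clause reads: "Subjects will be re-screened if there is a delay of more than 4 weeks between screening and participation". A parenthesis then sets a longer window for part of the work-up: "and the physical exam and laboratory tests will be repeated if older than 3 months". The sentence does not define laboratory tests or say what a re-screen contains.

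Study Procedures lists the screening medical evaluation as history, physical and "routine blood tests [including blood pregnancy test for females], urine toxicology, and EKG". The pregnancy test is thus explicitly one of the blood tests, while urine toxicology is a separate item in the same evaluation.

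Two exclusion criteria depend on these results. Exclusion 6 (pregnant or nursing) has no time point and is ascertained by interview, examination and a blood test. Part of exclusion 8 is "positive urine toxicology at screening", ascertained by interview and urine toxicology; the SAP's criteria list also ties it to screening.

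On risk, the protocol says: "The effects of nabilone have not been studied in pregnant or nursing women".

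**The concern.** A pregnancy test and a drug screen describe the patient on the day of the test, and either result can change soon afterwards. The protocol treats screening as stale after 4 weeks, yet lets laboratory results carry over for about three times as long. For a patient in that interval, the re-screen can be completed without renewing the one objective check on pregnancy, for a drug that the protocol describes as unstudied in pregnancy.

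Toxicology bears on interpretation. The SAP's primary outcomes include nabilone's tolerability and the Y-BOCS, assessed in two open-label arms of 10 with no placebo. Someone who resumed cannabis after the screening test could tolerate nabilone differently or report different symptoms, and nothing in the analysis would separate that from an effect of the drug. The protocol also admits patients from a marijuana study if they test negative for THC after completing it, but sets no interval between that test and the first nabilone dose.

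**Working it through.** The plan states no figure to reproduce. The check is calendar arithmetic on the two windows, followed by a search for a later test.

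**Inputs**
- Re-screening limit: 4 weeks = 4 × 7 = 28 days (Concurrent Research Studies).
- Laboratory allowance: 3 months, taken as 13 weeks = 13 × 7 = 91 days (same sentence).
- Treatment: 4 weeks = 28 days (Study Procedures).
- Assumption: the age of a result is counted to the first dose. The sentence says only participation.

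**What the rule does at each delay**
- Day 0 to 28: nothing is repeated.
- Day 29 to 91: the patient is re-screened, but the physical exam and laboratory tests may be carried over. Length of this interval: 91 − 28 = 63 days, or 9 weeks.
- After day 91: the laboratory tests are repeated.

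**Oldest result permitted**
- At first dose: 91 days (13 weeks), against 28 days if the re-screening limit applied. Ratio: 13 / 4 = 3.25.
- At the end of treatment, with no test in between: 91 + 28 = 119 days (17 weeks).

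**Does anything later close the gap?**
- Study Procedures: a baseline evaluation precedes randomization and weekly psychiatrist visits follow. Neither names a pregnancy or toxicology test.
- Assessment Instruments: the measurements listed for each visit are weight and vital signs.
- Blood and other Biological Samples: the entry on "proposed collection of blood or other biological specimens" is N/A. Specimens might be collected under the separate screening protocol, so this does not prove that no test exists. It does mean that none is scheduled here.
- Criteria for Early Discontinuation: pregnancy is a listed reason, but no test is attached to it.
- Research Related Delay to Treatment: patients are contacted weekly and removed if they come to meet an exclusion criterion. No test is attached here either. The contact runs from signing consent, which Study Procedures places after the medical evaluation, so any delay between the tests and consent has no stated contact.

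**What remains for each criterion between day 29 and day 91**
- Exclusion 6: of its three methods, the blood test and the physical examination can both be carried over. Interview is the part that the rule does not let carry over.
- Exclusion 8: if toxicology counts as a laboratory test, interview again remains. If it belongs to the re-screen, a new result is obtained. The sentence supports either reading; the first is more likely, because toxicology sits in the same medical evaluation as the other tests.

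**The case against.** The strongest reply is that the criteria do not rest on laboratory results alone. Exclusions 6 and 8 both use interview, the re-screen after 4 weeks still takes place, and the protocol removes anyone who later meets an exclusion criterion. This stands as partial cover. It does not replace the test, because the protocol itself chose to add an objective test to interview for both criteria.

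The second reply is that screening runs under another IRB protocol, which may set its own validity rules for tests. That cannot be excluded. However, this protocol cites it as 7094R under Concurrent Research Studies and as 6112R under Consent Procedures, so the reader cannot tell where such rules would be found.

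Several stronger readings are tempting but unsupported:
- A reader might infer that exclusion 8 goes unverified. As worded, a negative screening result satisfies its toxicology part. The weakness is that this part does not reach use after screening. Other criteria, such as the past-year substance use disorder exclusion and the requirement to be off most psychotropic drugs, still apply by interview.
- A reader might infer that a woman who conceives after the test is eligible. She is not: inclusion 2 and exclusion 6 have no time limit. She could be undetected, which is a different matter.
- A reader might infer from inclusion 2 that the contraceptive restrictions it mentions were never written. Part of the protocol was removed before publication, so their absence cannot be asserted.
- A reader might want an expected number of undetected pregnancies. The documents give neither the number of delayed starters nor a conception rate, and the age range runs to 60, so any count would come from assumptions.

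**Conclusion.** The concern holds in a limited form. Followed as written, the rule lets a patient delayed between about 4 and 13 weeks start nabilone on a blood pregnancy test up to about 91 days old, 3.25 times the age that the 4-week limit would allow. Exclusion 6 is then not confirmed by a current laboratory test, although interview and later removal still apply. This rests on the pregnancy test being a laboratory test, which Study Procedures makes plain, and on the separate screening protocol containing no stricter rule, which cannot be checked.

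For urine toxicology the conclusion is weaker: coverage by the 3-month allowance is likely but unstated, and exclusion 8 leaves use between screening and first dose outside its toxicology part. With 10 patients per arm, one such patient would be 1/10 = 10% of an arm. That shows how little it takes to affect the result; it is not evidence that any such patient would enrol.

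Only starts delayed beyond 4 weeks are affected, and their number is unknown. The point is worth correcting because the gap lies in a single sentence and is easily closed.

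**What to change.** Amend the sentence under Concurrent Research Studies so that the blood pregnancy test and urine toxicology are outside the 3-month allowance and form part of the re-screen already required after 4 weeks. List the tests that stay under the 3-month allowance, and say to which date the age of a result is counted. Reword exclusion 8, in the protocol and in the SAP's criteria list, to refer to the most recent screening or re-screening result. Cite the screening protocol under one IRB number and state whether it sets test-validity rules of its own.

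The cost is a wording amendment, a repeat of two inexpensive tests already in the plan for delayed starters only, and an occasional patient who fails the re-screen. The change makes the protocol's two windows and the two exclusions consistent. It does not address testing during treatment, on which no rule is proposed here.
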